### 8.4.2 Serious Adverse Event Reporting

If an event occurs and is determined to be a SAE, it will be documented and monitored as described for AE's, with the addition that the Investigator will notify the IRB directly within 1 business day. Appropriate acute medical care will be provided to the subject.

### 8.4.3 Unanticipated Problem Reporting

Incidents or events that meet the OHRP criteria for UPs require the creation and completion of an UP report form. It is the site investigator's responsibility to report UPs to their IRB The UP report will include the following information:

- Protocol identifying information: protocol title and number, PI's name, and the IRB project number;
- A detailed description of the event, incident, experience, or outcome;
- An explanation of the basis for determining that the event, incident, experience, or outcome represents an UP;
- A description of any changes to the protocol or other corrective actions that have been taken or are proposed in response to the UP.

To satisfy the requirement for prompt reporting, UPs will be reported using the following timeline:

- UPs that are SAEs will be reported to the IRB within 1 week of the investigator becoming aware of the event.
- Any other UP will be reported to the IRB within 1 week of the investigator becoming aware of the problem.
- All UPs should be reported to appropriate institutional officials (as required by an institution's written reporting procedures), the supporting agency head (or designee), and OHRP within 1 week of the IR's receipt of the report of the problem from the investigator.

### 8.4.4 Reporting of Pregnancy

Patients who are pregnant will not be included in this study.

### 8.5 Reporting Procedures – Participating Investigators

This is not a multi-center clinical trial.

### 8.6 Study Halting Rules

Not applicable.

# 8.7 Safety Oversight

Study number: i20-00356 Page 23 Version: June 8, 2020

It is the responsibility of the Principal Investigator to oversee the safety of the study at his/her site. This safety monitoring will include careful assessment and appropriate reporting of adverse events as noted above, as well as the construction and implementation of a site data and safety-monitoring plan. Medical monitoring will include a regular assessment of the number and type of serious adverse events.

# 9 Clinical Monitoring

Clinical site monitoring is conducted to ensure that the rights and well-being of human subjects are protected, that the reported trial data are accurate, complete, and verifiable, and that the conduct of the trial is in compliance with the currently approved protocol/amendment(s), with GCP, and with applicable regulatory requirement(s).

- The PI will conduct on-site monitoring for initial assessment with a comprehensive review of the data.
- Independent audits will be conducted by the sub-investigators to ensure monitoring practices are performed consistently across all participating sites.
- Each clinical site will perform internal quality management of study conduct, data collection, documentation and completion. An individualized quality management plan will be developed to describe a site's quality management.

### 10 Statistical Considerations

### 10.1 Statistical and Analytical Plans (SAP)

A formal SAP will be completed prior to database lock.

# 10.2 Statistical Hypotheses

We hypothesize that there will be no difference in the diagnostic accuracy of the Arthrex NanoScope compared to conventional arthroscopic instruments.

### 10.3 Description of Statistical Methods

### 10.3.1 General Approach

Descriptive statistics will be used to provide a quantitative summary of the data in the study. Specifically, the analysis performed included measures of central tendency (mean, median, and mode) and measures of variability (range and standard deviation). Categorical data will be described in percentages and a Chi-squared test will be employed to detect if these categorical variables are related between the two treatment groups with a p value of < .05. Continuous data will be described in means with standard deviations. A two -tailed Student's T-test will be employed to compare the means between the two treatment groups with a p value of < .05.

Version: June 8, 2020

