### 4.2 Study Endpoints

### 4.2.1 Primary Study Endpoints

The primary endpoint will be diagnostic accuracy (%) compared to the gold standard of conventional wrist arthroscopy instruments.

The primary endpoint was chosen to determine if smaller instrumentation provides adequate visualization for the diagnosis of wrist pathology and can therefore be used as the sole means of evaluation.

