### 10.3.2 Analysis of the Primary Efficacy Endpoint(s)

### **Primary**

1. Diagnostic accuracy of Nanoscope compared to conventional arthroscope.

Diagnostic accuracy of the Arthrex Nanoscope will be described as a incidence/percentage compared to the diagnosis determined by wrist arthroscopy with conventional instruments.

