### 10.4 Sample Size

34 participants will be recruited to meet a goal of evaluable participants for the study.

- Outcome measure: diagnostic accuracy
- Test statistic: descriptive statistics

Study number: i20-00356 Page 25 Version: June 8, 2020

• Null hypothesis: We hypothesize that there will be no difference in the diagnostic accuracy of the Arthrex NanoScope compared to conventional arthroscopic instruments.

• Type I error rate (alpha): 0.95

Power level: 0.819

Dropout: Not applicable.

• Approach to handling withdrawals and protocol violations: Not applicable.

Statistical method used to calculate the sample size: At 90% prevalence, in order to detect a change in sensitivity (true-positive) between .70 (sensitivity of MRI) and .90 (sensitivity of arthroscopy), we would need a minimum of 34 subjects with a minimum of 31 who had a ligamentous wrist injury (see table below). This was determine with the guidance of the Center for Clinical Research.

Mohamad Adam Bujang and Tassha Hilda Adnan, Requirements for Minimum Sample Size for Sensitivity and Specificity Analysis

www.jcdr.net

H a 0.60 0.70 0.80 0.90 0.70 0.80 0.90 0.90 0.90 0.90 0.95 0.60 0.70 0.80	Power 0.804 0.810 0.804 0.889 0.801 0.826 0.885 0.818 0.807 0.819 0.816 0.804 0.804	p-value 0.047 0.044 0.041 0.039 0.048 0.034 0.035 0.044 0.048 0.040 0.048	N1 199 49 20 12 181 45 19 155 31 107 231 199	N 284 70 29 17 259 64 27 221 44 153 330		Perv 70% 70% 70% 70% 70% 70% 70% 70% 70% 70%	H o 0.50 0.50 0.50 0.50 0.60 0.60 0.60 0.70	H a 0.60 0.70 0.80 0.90 0.70 0.80 0.90 0.80 0.90	0.804 0.810 0.804 0.889 0.801 0.826 0.885 0.818	p-value 0.047 0.044 0.041 0.039 0.048 0.034 0.035 0.044	N1 464 114 47 28 422 105 44 362	N 663 163 67 40 603 150 63 517
0.70 0.80 0.90 0.70 0.80 0.90 0.90 0.90 0.95 0.60	0.810 0.804 0.889 0.801 0.826 0.885 0.818 0.807 0.819 0.816 0.804 0.804	0.044 0.041 0.039 0.048 0.034 0.035 0.044 0.048 0.040 0.048 0.047	49 20 12 181 45 19 155 31 107 231	70 29 17 259 64 27 221 44 153 330		70% 70% 70% 70% 70% 70% 70% 70%	0.50 0.50 0.50 0.60 0.60 0.60 0.70	0.70 0.80 0.90 0.70 0.80 0.90	0.810 0.804 0.889 0.801 0.826 0.885 0.818	0.044 0.041 0.039 0.048 0.034 0.035	114 47 28 422 105 44 362	163 67 40 603 150 63

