### 10.5 Measures to Minimize Bias

### 10.5.1 Enrollment/Randomization/Masking Procedures

Enrollment will not be randomized. Each patient will serve as an internal control.

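### The chi-squared test, the only test named for categorical data, cannot address the hypothesis of no difference in diagnostic accuracy; use the paired cross-table with exact intervals.

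*Combined protocol and SAP*

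**What the plan says.** Section 10.2 states the hypothesis: "We hypothesize that there will be no difference in the diagnostic accuracy of the Arthrex NanoScope compared to conventional arthroscopic instruments". It gives no margin.

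Section 10.3.1, repeated in the Statistical Analysis row of the Protocol Summary, says that for categorical data "a Chi-squared test will be employed to detect if these categorical variables are related between the two treatment groups", at the .05 level. The only other test named in sections 10.3.1 to 10.3.3 is a t-test for means, which section 10.3.3 repeats for the surgeon ratings.

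The groups in question are not separate patients. Section 4.1 describes a single cohort examined first with the NanoScope and then with conventional instruments, and section 10.5.1 says "Each patient will serve as an internal control". Section 4.2.1 makes the conventional scope the reference: "The primary endpoint will be diagnostic accuracy (%) compared to the gold standard of conventional wrist arthroscopy instruments".

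The sections on the primary endpoint are descriptive. Section 10.3.2 says that accuracy "will be described as a incidence/percentage compared to the diagnosis determined by wrist arthroscopy with conventional instruments", and section 10.4 gives "Test statistic: descriptive statistics". Sensitivity and specificity are listed in the Protocol Summary objectives and under Final Assessments in the study schematic. No confidence interval is mentioned for any of these quantities. Section 10.1 defers a formal SAP to before database lock.

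**The concern.** A diagnosis is categorical, so a reader looking for the test that goes with section 10.2 finds only the chi-squared test. It can be laid out in two ways.

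- **Scope by finding** (NanoScope positive/negative against conventional positive/negative). The null is that both scopes call the same proportion positive. Whether they agree on a given wrist is never used, so a miss in one wrist cancels a false call in another.
- **NanoScope reading by conventional reading.** The null is that the two readings are unrelated. Good agreement produces a small p-value, so significance here is evidence of association and not of a difference.

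Neither null is equal accuracy. The conventional scope is the reference and is 100% accurate by definition, so no difference in accuracy means wrist-by-wrist agreement.

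Section 4.2.1 says the endpoint was chosen to judge whether the smaller scope could be used on its own. A p-value that says nothing about agreement should not be available as support for that conclusion.

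**Working it through.** **Inputs.** From section 10.4: 34 wrists, 31 with ligamentous injury, prevalence 90%, sensitivities 0.70 and 0.90. From section 10.3.1: level .05. Other prevalences, and other sensitivity/specificity values, are assumptions. The unit of analysis (wrist or structure) is not stated; one binary reading per wrist is used here.

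**The plan's own figure.** The 0.70 versus 0.90 row of the section 10.4 table is an exact two-sided one-sample binomial test. With n = 31, it rejects at 16 or fewer or at 27 or more positives, giving alpha 0.0478 and power 0.807. This matches the row (0.048, 0.807), and 31/0.9 = 34.4. That calculation tests sensitivity against a fixed value and is not the chi-squared test of section 10.3.1.

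**A NanoScope unrelated to the wrist.** Suppose it calls 90% of wrists positive regardless of their state, so sensitivity is 0.90 and specificity 0.10. Expected agreement is 0.9 × 0.9 + 0.1 × 0.1 = 0.82. With 31 injured and 3 uninjured wrists, the rounded cross-table has 28 true positives, 3 misses, 3 false calls and 0 true negatives.

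- Agreement: 28/34 = 82%. Specificity: 0/3.
- Positive rates: 31/34 against 31/34, so chi-squared = 0 and p = 1.0.
- Independence: 34 × (28×0 − 3×3)² / (31×3×31×3) = 2754/8649 = 0.32, p = 0.57.
- McNemar: (3 − 3)²/(3 + 3) = 0.

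**A perfect NanoScope.** The cross-table is 31/0/0/3. The independence chi-squared is 34 × (31×3)² / (31×3×31×3) = 34, p = 5.5e-9. It fails to reject only when a sample has no uninjured wrist: 0.9^34 = 0.028, so it rejects about 97% of the time.

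**Rejection rates.** The number injured is Bin(34, prevalence), true positives Bin(injured, sensitivity) and true negatives Bin(uninjured, specificity). The test is the uncorrected chi-squared on positive rates.

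| Prevalence | Sens. / spec. | Accuracy | Rejects |
|---|---|---|---|
| 90% (plan) | 0.90 / 0.10 | 82% | about 6% |
| 90% (plan) | 0.50 / 0.50 | 50% | 97% |
| 90% (plan) | 0.70 / 0.70 | 70% | 73% |
| 90% (plan) | 0.70 / 0.90 | 72% | 81% |
| 50% (assumed) | 0.50 / 0.50 | 50% | 4.4% |
| 50% (assumed) | 0.70 / 0.70 | 70% | 1.1% |
| 30% (assumed) | 0.70 / 0.87 | 82% | 0.4% |

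McNemar's test rejects the 0.90/0.10 scope about 5% of the time, because it too compares only positive rates.

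**How far a non-significant result can stretch at 31 injured and 3 uninjured.** With 9 misses and 3 false calls the NanoScope has 22 + 3 = 25 positives and accuracy 22/34 = 65%. Chi-squared = 68 × (25×3 − 9×31)² / (34×34×56×12) = 3.64, below the 3.84 critical value.

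**What intervals show.** If true accuracy is 70%, the exact 95% interval for the percentage lies wholly below 90% in 84% of trials of 34. For 28/34 the interval is 65% to 93%, so the accuracy interval alone does not expose the 0.90/0.10 scope. Nor does sensitivity, which would pass the section 10.4 test about 81% of the time. Only specificity can expose it, and with 3 uninjured wrists the exact interval is 0% to 71% for 0/3 and 29% to 100% for 3/3.

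**The case against.** The best defence is that the plan never attaches this test to the primary endpoint. Section 10.3.1 is a general statement, while section 10.3.2 names no test and section 10.4 calls the statistic descriptive. The authors repeat the t-test in section 10.3.3 where they want one, and did not do the same with chi-squared in section 10.3.2. Sensitivity and specificity are already planned and would reveal misses and false calls. Section 10.4 contains a calculation that does concern accuracy against the reference. A formal SAP is still to come. All of this stands, and it limits the point.

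Two stronger readings are tempting.

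- A reader might infer that a coin-flip NanoScope would pass as showing no difference. At the plan's 90% prevalence it would not: 17/34 against 31/34 positives gives chi-squared 13.9, p = 0.0002, and such a scope is rejected about 97% of the time. It passes mainly when prevalence is near 50%, which the documents do not state. Section 7.1.1 lists ten structures whose individual prevalences are not given, so lower values are possible but unsupported.
- A reader might infer that the sponsor will report a non-significant chi-squared as proof of equal accuracy. No section says so. Under the independence layout, a small p-value correctly means that the readings are related; it misleads only if misread.

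The defence does not supply an inferential analysis for section 10.2, and nothing in section 10.3.1 excludes the diagnoses from the chi-squared test. The usual correction from an unpaired to a paired test would leave the same gap.

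**Conclusion.** The point holds in a limited form. Chi-squared is the only test the methods section offers for the diagnoses, and neither null it can carry is the one in section 10.2. The size at the plan's own 90% prevalence and 34 wrists is this: a scope whose readings carry no information about the wrist, but which calls 90% positive, is rejected about 6% of the time on positive rates, and a perfect scope gives p < .05 about 97% of the time on independence. The failure is specific to errors in both directions; errors mainly in one direction are usually detected (81% at sensitivity 0.70, specificity 0.90).

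These figures assume one binary reading per wrist, independent wrists and no continuity correction. Because the primary endpoint is already a descriptive percentage, this should be fixed, but it does not invalidate the planned primary analysis.

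**What to change.** In section 10.3.1 and the Protocol Summary, state that the chi-squared test is not used to compare the two scopes' diagnoses and that no conclusion about accuracy rests on it.

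In section 10.3.2, or in the SAP, base the section 10.2 conclusion on the paired NanoScope-by-conventional cross-table:

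- the accuracy percentage, sensitivity and specificity, each with an exact 95% interval;
- misses and false calls as separate counts;
- the unit of analysis, with intervals that allow for clustering within a wrist if structures are analysed.

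If McNemar's test is reported, label it a test of call rates only.

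The cost is wording; both readings are already recorded for every wrist. The paper loses a p-value and shows wide intervals, most of all for specificity with about 3 uninjured wrists. That width reflects what 34 wrists at 90% prevalence can support.

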Number of participants	34
Description of Study Agent/Procedure	The Arthrex NanoScope is a 1.9 mm wrist arthroscopy system.
Reference Therapy	Conventional wrist arthroscope
Key Procedures	Diagnostic wrist arthroscopy of wrists with clinical and imaging confirmation of internal derangement (ligament/articular/bony injury).
Statistical Analysis	Descriptive statistics will be used to provide a quantitative summary of the data in the study. Specifically, the analysis performed included measures of central tendency (mean, median, and mode) and measures of variability (range and standard deviation). Categorical data will be described in percentages and a Chi-squared test will be employed to detect if these categorical variables are related between the two treatment groups with a p value of < .05. Continuous data will be described in means with standard deviations. A two-tailed Student's T-test will be employed to compare the means between the two treatment groups with a p value of < .05.

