# 6 Study Agent (Study drug, device, biologic, vaccine etc.) and/or Procedural Intervention

The procedural intervention will be a diagnostic wrist arthroscopy using the Arthrex NanoScope followed by a diagnostic wrist arthroscopy using conventional wrist arthroscopy equipment.

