### 6.3.2 Procedures for Training of Clinicians on Procedural Intervention

The intervention will be standardized by having a single operator (attending) perform the diagnostic arthroscopy with the Arthrex NanoScope and conventional instruments. The diagnostic arthroscopy will be performed in a stepwise manner evaluating the ligaments and articular surfaces of the wrist.

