### 10.3.3 Analysis of the Secondary Endpoint(s)

### Secondary

- 1. Incidence of change in intervention.
- 2. Surgeon rated ease of use.
- 3. Surgeon rated confidence of diagnosis.
- 4. Correlation between pre-operative MRI findings and arthroscopic findings.

Secondary endpoints will be described using incidence/percentage. A two-tailed Student's T-tests will be employed to compare the means of surgeon-rated outcomes between the Arthrex NanoScrope and conventional instruments groups with a p value of .05.

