### 10.3.6 Baseline Descriptive Statistics

Not applicable. Each patient will serve as an internal control.

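### Both scopes are used in every wrist, but the plan names only two-group tests, so surgeon-rating p-values are wrong unless paired ratings are uncorrelated

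*Combined protocol and SAP*

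**What the plan says.** The design sections describe within-patient pairs. Section 4.1 has a single cohort with the NanoScope as step 1 and conventional instruments as step 2. Section 6 defines the procedure as "a diagnostic wrist arthroscopy using the Arthrex NanoScope followed by a diagnostic wrist arthroscopy using conventional wrist arthroscopy equipment". Section 6.3.2 standardises it by "having a single operator (attending) perform the diagnostic arthroscopy with the Arthrex NanoScope and conventional instruments". Section 10.5.1 states: "Enrollment will not be randomized. Each patient will serve as an internal control". Section 10.3.6 makes the same point about internal control.

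The analysis sections describe independent groups. For continuous data, section 10.3.1 plans that a Student's "T-test will be employed to compare the means between the two treatment groups". For categorical data, "a Chi-squared test will be employed to detect if these categorical variables are related between the two treatment groups". The Protocol Summary carries the same text. Section 10.3.3 applies the t-test to a named endpoint, to "compare the means of surgeon-rated outcomes between the Arthrex NanoScrope and conventional instruments groups with a p value of .05".

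No paired t-test, signed-rank test, McNemar's test or other within-patient method is named. Section 10.1 promises a formal SAP before database lock but says nothing about its content.

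**The concern.** A two-sample test takes the two sets of ratings as independent. Here the same surgeon rates the same wrist twice in one session, so the two ratings probably move together: a tight or badly damaged wrist is hard with either scope. The two-sample standard error is then too large, and a real difference in ease of use or confidence is more likely to be missed. If the ratings move in opposite directions, the standard error is too small and the error rate exceeds 5%.

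The reach is limited. The primary endpoint in section 10.3.2 is a descriptive percentage. Change in intervention is one proportion per patient. The explicit problem is the surgeon-rating comparison in section 10.3.3, the only hypothesis test the plan attaches to named endpoints. The same fault would carry over to any categorical comparison between scopes run under the general rule in section 10.3.1.

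**Working it through.** **Inputs from the documents.** n = 34 pairs (section 5.6); two-tailed test at 0.05 (10.3.3); 5-point ratings (7.1.1). The documents give no SD, effect size or within-patient correlation ρ, so these are assumed and varied.

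**The plan's own figure.** Section 10.4 derives 34 subjects, 31 with injury, from sensitivity 0.70 versus 0.90 at 90% prevalence. An exact binomial test with n = 31 that rejects at 16 or fewer or 27 or more has alpha 0.048 and power 0.807, as in the table row used, and 31/0.90 = 34.4. So N reproduces. It does not depend on the surgeon ratings, and the present point leaves it unchanged.

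**Variance.** With common SD σ, the true variance of the difference in means is 2σ²(1 − ρ)/n. The two-sample t-test uses 2σ²/n. The true standard error is therefore √(1 − ρ) times the one used, and in large samples

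type I error = 2[1 − Φ(1.96/√(1 − ρ))].

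At ρ = 0.5: 1.96/0.707 = 2.77, giving 0.006. At ρ = −0.3: 1.96/1.140 = 1.72, giving 0.086.

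**Power.** For a difference of d SDs, the unpaired statistic is centred at about d√(n/2) and the paired one at d√(n/[2(1 − ρ)]). With d = 0.5 and ρ = 0.5 these are 0.5 × √17 = 2.06 and 0.5 × √34 = 2.92. The degrees of freedom are 66 and 33.

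Simulation with 34 bivariate normal pairs (at least 100,000 trials per setting):

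| ρ | Type I, unpaired (formula) | Type I, unpaired (simulated) | Power at 0.5 SD, unpaired | Power at 0.5 SD, paired |
|---|---|---|---|---|
| −0.3 | 0.086 | 0.084 | 0.53 | 0.42 |
| 0 | 0.050 | 0.050 | 0.53 | 0.52 |
| 0.3 | 0.019 | 0.020 | 0.53 | 0.67 |
| 0.5 | 0.006 | 0.007 | 0.54 | 0.81 |
| 0.7 | 0.0003 | 0.0006 | 0.55 | 0.95 |

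The paired t-test keeps a type I error of about 0.05 in every row. The higher unpaired power at ρ = −0.3 comes with the inflated error rate. At ρ = 0.5, power unpaired versus paired is 0.15 versus 0.40 for 0.3 SD, and 0.96 versus 0.99 for 0.8 SD.

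**Five-point scores.** Latent normals were cut at −2, −1.3, −0.5 and 0.5, with latent ρ 0.5 and one scope shifted 0.5 lower. Power is 0.48 for the unpaired t-test, 0.72 for the paired t-test and 0.71 for the Wilcoxon signed-rank test. Type I errors are 0.010, 0.052 and 0.049.

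**Binary illustration (invented counts).** Suppose a finding is seen by both scopes in 20 patients, NanoScope only in 0, conventional only in 6 and neither in 8. The difference is 26/34 − 20/34 = 17.6 points.

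- Unpaired: 95% CI −4.2 to 39.5; chi-squared p = 0.120.
- Paired: SE = √(6 − 36/34)/34 = 0.065; 95% CI 4.8 to 30.5; exact McNemar p = 2 × 0.5⁶ = 0.031.

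With counts 20, 1, 6 and 7 the p-values are 0.19 and 0.125, so pairing does not always change the conclusion.

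**The case against.** **Student's t-test has a paired form.** The plan never says independent or unpaired, and twice calls the patient an internal control. The methods paragraph reads like template text, and a SAP is still to come. This stands as a reason to treat the defect as correctable wording. It does not remove it: comparing means between groups is two-sample language, the chi-squared sentence has no paired reading, and nothing says that the SAP will differ.

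**No between-scope binary test is listed.** The conventional scope is the reference standard, so the binary part concerns only what the general rule would permit. That is right, and the counts above are illustrative.

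**In the likely case the test is conservative.** With positive correlation the fault is lost power, not excess false positives, and its size is unknown because every correlation and effect size is assumed. At ρ = 0 pairing gains nothing. All of this is true. The paired test costs about one point of power there and holds its level throughout.

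**Pairing does not cure everything.** Patients come from several practices and four sites, and the single operator may mean one attending per case. If four surgeons share 34 patients equally, and within-patient differences have a surgeon-level intraclass correlation (ICC) of 0.05, 0.1 or 0.2, the paired t-test's type I error is about 0.09, 0.14 or 0.22. With eight surgeons it is about 0.07, 0.09 or 0.13. The NanoScope always goes first, so no test can separate scope from order. These points stand as further limits. Neither favours the two-sample test.

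**Conclusion.** The concern holds and should be fixed. The documents describe a paired design and name only two-group tests. Applied as written, the surgeon-rating t-test has its nominal 5% level only at zero within-patient correlation. For correlations from 0.3 to 0.7 its true level is 2% down to below 0.1%, and for a 0.5 SD difference it gives up roughly 14 to 40 points of power. At −0.3 its level is 8.4%. These sizes assume 34 complete pairs, equal SDs, independent patients and the stated correlations, none of which the documents supply. That the unpaired standard error is wrong whenever the correlation is not zero needs no assumed size. The consequence is confined to secondary endpoints and to any categorical between-scope comparison made under section 10.3.1.

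**What to change.** In section 10.3.1, section 10.3.3, the Protocol Summary and the pending SAP:

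1. Replace the reference to two treatment groups with two scopes in the same patient.
2. Test the within-patient difference in each 5-point rating with a paired t-test or Wilcoxon signed-rank test, chosen in advance, and report the mean difference with a 95% CI. If several attendings take part, say how clustering by surgeon is handled.
3. For any patient-level binary comparison between scopes, use McNemar's test and the paired difference with a 95% CI.
4. Keep sensitivity and specificity against the conventional scope, with 95% CIs, as the accuracy analysis. McNemar's test cannot replace it: with 6 misses and 6 false calls in 34 patients it gives p = 1.0, while agreement is only 22/34 = 65%.
5. If findings are analysed by structure (ten per wrist in section 7.1.1), allow for clustering within the wrist, for example by bootstrapping patients. At an assumed ICC of 0.1 the design effect is 1 + 9 × 0.1 = 1.9, so 340 structure-level pairs carry the information of 340/1.9 = 179.
6. State that the questionnaire is completed once per scope. The Schematic of Study Design lists ease of use and confidence under each scope, but section 7.1.1 mentions one short questionnaire after the procedure. Settle this before enrolment, because a later SAP cannot recover ratings that were not collected.

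The cost is wording plus a check of the form. N = 34 and the software are unchanged. A structure-level analysis would also need its unit and clustering method defined.
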